## 4 Study Design

This is a phase 2, prospective, non-randomized, matched-pair, single center study designed to evaluate the safety and efficacy of PAE using Embosphere Microspheres as a pre-operative tool in patients with biopsy-proven adenocarcinoma of the prostate with localized disease. A total of 10 patients with biopsy-proven prostate carcinoma with localized disease will be enrolled in the study to receive pre-prostatectomy PAE, and matched with 10 controls who will not receive pre-prostatectomy PAE, in order to evaluate the study objectives. Patient recruitment is anticipated to take approximately 2 years. Duration of participation is expected to be approximately 15 months from time of enrollment, including a minimum of 12 months follow up. This study will have a stop limit for re-evaluation after two patients with serious adverse events attributed to confirmed or suspected non-target embolization have been identified.

### 4.1 PAE Patients

The study will consist of a screening period in which patient eligibility will be determined. Consecutive eligible patients will be offered study participation to receive PAE with Embosphere Microspheres pre-RALRP. All patients will provide written informed consent before any study-specific assessments are performed. Patients will complete Expanded Prostate Cancer Index Composite (EPIC) and International Index of Erectile Function (IIEF) questionnaires, and undergo a baseline MRI with contrast to evaluate the size of the prostate gland and stage the cancer. Ten eligible patients will be enrolled and will undergo PAE with Embosphere Microspheres within 4 weeks of baseline imaging. After PAE treatment, patients will return for follow-up visits at 2 weeks ( $\pm 4$  days) and 6 weeks ( $\pm 2$  weeks) post embolization. Post-prostate artery embolization cystoscopy and rectoscopy will be performed during any visit up to 12 months post RALRP, if medically indicated especially if there is pain out of proportion to that which is expected, in all cases of bleeding per the rectum, and in cases of hematuria beyond that which is reasonably expected following prostatectomy. At 6 weeks patients will complete the EPIC and IIEF questionnaires, receive a physical exam, and undergo laboratory assessments (including PSA levels), DRE, TRUS and an MRI of the prostate. The patients will undergo RALRP at 10 weeks ( $\pm 2$  weeks) post PAE, and will have first post-op follow up visit at 12 days  $\pm 7$  days for urinary catheter removal. The impact of the embolization procedure on the perioperative, oncologic and functional outcomes will be evaluated at follow-up visits at 3, 6, 9 and 12 months post RALRP. Subsequent annual follow up will be performed as per standard protocol for the treating institution.

### 4.2 Control Patients

A similar cohort of patients who undergo RALRP without PAE will be treated as a matched control group. The controls will be matched using a 1:1 ratio to PAE treated patients based on AUA risk group. Risk stratification will be as follows, according to AUA guidelines:

- Low risk: Stage T1c to T2a tumors, AND PSA  $\leq 10$ ng/mL, AND Gleason score  $\leq 6$

- Intermediate risk: Stage T2b tumors, OR PSA > 10ng/mL but ≤ 20ng/mL, OR Gleason score 7
- High risk: Stage T2c or higher tumors, OR PSA > 20ng/mL, OR Gleason score 8-10

Control patients will be selected after 10 patients for the PAE arm have been identified, such that the first potential control patient who matches the risk score of a PAE patient and agrees to participate in the study is matched to the appropriate member of the PAE arm. Once a match is identified, additional matches for a single PAE patient will not be sought. Because we are matching PAE and control patients based on AUA risk score only, we do not anticipate difficulty in finding a matched control for every PAE patient.

Control patients will sign written informed consent before any study-specific assessments are performed. Patients will complete EPIC and IIEF questionnaires within 12 weeks prior to RALRP, and will undergo MRI as a baseline study. Oncologic and functional outcomes will be evaluated by assessing PSA, EPIC, and IIEF at months 3, 6, 9, and 12 post RALRP, and then annually per standard follow-up protocol for the treating institution.

Safety will be evaluated for PAE patients throughout the study treatment and assessment periods by assessing adverse events, concomitant medications, changes in laboratory values, and findings on physical examination. Safety will be evaluated for Control patients during RALRP and the follow up period by assessing adverse events and concomitant medications.

The patients in both groups will continue to be followed post RALRP according to standard follow up protocol for the treating institution.

## 5 Treatment and Assessment

A Schedule of Study Events is provided in Appendix A, and a study flow chart is provided in Appendix B.

### 5.1 Visit -1: Screening/Baseline

#### **PAE Patients (Visit -1 must be within 4 weeks before PAE):**

Prior to treatment, patients in the PAE group will have the following assessments performed:

- Obtain Informed Consent
- Medical history, including demographics
- Physical exam, including vital signs, height (baseline only), weight, and genitourinary evaluation
- Recording of current medications
- Recording of concurrent medical conditions
- Prostate Specific Antigen (PSA)
- Urinalysis
  - Specific gravity, protein, glucose, blood, leukocytes, nitrites
- Baseline blood tests
  - Complete blood count (CBC) including red blood count (RBC), white blood count (WBC), platelets, hemoglobin, hematocrit, neutrophils
  - PT (Prothrombin Time)
  - Comprehensive metabolic panel
- Digital rectal exam (DRE) and transrectal ultrasound (TRUS)
- MRI of the prostate
- Expanded Prostate Cancer Index Composite (EPIC) Questionnaire
- International Index of Erectile Function (IIEF) Questionnaire

Patients meeting all the inclusion criteria and none of the exclusion criteria are eligible to receive pre-RALRP PAE.

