### **3 PAE Patient Population**

#### **3.1 Inclusion Criteria**

Patients must meet all of the following inclusion criteria in order to be entered into the study:

1. Patient is 45-79 years old
2. Patient has signed informed consent
3. Patient must have biopsy-proven prostate adenocarcinoma with localized disease
4. Patient must be a candidate for robot-assisted radical prostatectomy (RALRP)
5. Patient has a prostate size >40 grams

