### 3.2 Exclusion Criteria

Patients meeting any of the following exclusion criteria may not be entered into the study:

1. Active urinary tract infection
2. History of life threatening allergy to iodinated contrast agents
3. Any known condition that limits catheter-based intervention or is a contraindication to embolization (eg shunt or adverse arterial anatomy)
4. Patient is unable to undergo MRI imaging
5. Cardiac condition including congestive heart failure or uncontrolled arrhythmia, uncontrolled diabetes mellitus, significant respiratory disease, or known immunosuppression which required hospitalization within the previous 6 months.
6. Baseline serum creatinine level  $> 1.8$  mg/dL
7. Baseline hemoglobin  $< 8.0$  g/dL
8. Active cystolithiasis or prostatitis
9. History of pelvic irradiation or radical pelvic surgery
10. Known major iliac arterial occlusive disease
11. Confirmed or suspected bladder cancer
12. Urethral strictures, bladder neck contracture, or other bladder or urethral pathology that could limit catheterization
13. Previous rectal surgery (other than hemorrhoidectomy) or history of rectal disease if the therapy or patient evaluation may potentially cause injury to sites of previous rectal surgery, e.g. if a transrectal probe is used
14. Previous pelvic irradiation or radical pelvic surgery
15. Previous prostate surgery, balloon dilatation, stent implantation, laser prostatectomy, hyperthermia, or any other invasive treatment to the prostate
16. Prior transurethral resection of the prostate or other invasive therapies
17. Coagulation disturbances not normalized by medical treatment
18. Acute urinary retention
19. Hypersensitivity to gelatin products
20. Any contraindication to embolization, including intolerance to vessel occlusion procedures, vascular anatomy/blood flow that precludes catheter placement or embolic agent injection, presence/likely onset of vasospasm, presence/likely onset of hemorrhage, severe atheromatous disease, feeding arteries smaller than distal branches, arteriovenous shunt, and collateral vessel pathways endangering normal territories during embolization or pelvic inflammatory disease

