### **Control Patients (Visit -1 must be within 12 weeks prior to RALRP):**

Prior to RALRP patients in the Control group will have the following assessments performed:

- Obtain Informed Consent
- Medical History, including demographics
- Physical exam, including vital signs, height (baseline only), weight, and genitourinary evaluation
- Assessment that patient is a match for a PAE patient based on:
  - Low, intermediate or high risk prostate cancer based on AUA guidelines
- Recording of concurrent medical conditions
- Recording of current medications
- Prostate Specific Antigen (PSA)
- Urinalysis
  - Specific gravity, protein, glucose, blood, leukocytes, nitrites
- Baseline blood tests
  - Complete blood count (CBC) including red blood count (RBC), white blood count (WBC), platelets, hemoglobin, hematocrit, neutrophils
  - PT (Prothrombin Time)
  - Comprehensive metabolic Panel
- Expanded Prostate Cancer Index Composite (EPIC) Questionnaire
- International Index of Erectile Function (IIEF) Questionnaire
- Digital Rectal Exam (DRE) and TRUS of the prostate
- MRI of the prostate

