## Appendix A2: Schedule of Study Events for Control Patients

[figure not shown]
	Visit -1	Visit 4	Visit 5	Visits 6, 7, 8, 9
	Screening/ Baseline	RALRP (12 weeks $\pm$ 2 weeks from baseline)	12 days (+/-7 days) post RALRP	Months 3, 6, 9, 12 $\pm$ 2 weeks post RALRP
Informed Consent	X			
Matching Assessment	X			
Demographics	X			
Medical History	X			
Concurrent Medical Conditions	X			
Physical Examination	X		X	X
Vital Signs	X		X	X
Complete Blood Count (CBC)	X	X 	X	
Serum Chemistry	X		X	
Prostate Specific Antigen (PSA)	X			X
Urinalysis	X		X	
Digital Rectal Exam (DRE)	X			
Transrectal Ultrasound (TRUS)	X			
MRI of the Prostate	X			
EPIC Questionnaire	X			X
IIEF Questionnaire	X			X
Pad Weight Test				X
RALRP Procedure		X		
Post-RALRP Evaluation		X 		
Hematocrit & Hemoglobin		X 		
Adverse Events			X	
Concomitant Medications			X	
Protocol Violations			X	

 CBC on day of RALRP must be performed prior to surgery

 Post-RALRP includes duration of hospital stay, post treatment catheter duration, and pathologic/histopathology assessment

[figure not shown]
 Hemoglobin and hematocrit will be measured 1 day post RALRP

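### No eligibility criteria are operationally applied to controls, including prostate size, so the arms can differ on factors that affect surgery, with blood-loss bias of uncertain direction

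*Combined protocol and SAP*

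**What the plan says.** The criteria stand in section 3, headed "PAE Patient Population"; no section sets criteria for controls. The lead-in sentences are wider than the heading. Section 3.1 begins "Patients must meet all of the following inclusion criteria in order to be entered into the study", and 3.2 begins "Patients meeting any of the following exclusion criteria may not be entered into the study".

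The procedures follow the heading. For PAE patients, 5.1 ends its Visit -1 list with "Patients meeting all the inclusion criteria and none of the exclusion criteria are eligible to receive pre-RALRP PAE". The control list has no such sentence. It has "Assessment that patient is a match for a PAE patient based on", followed by the AUA risk group alone. Appendix A1 has a row for an eligibility assessment; at that place Appendix A2 has "Matching Assessment".

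Section 4.2 matches 1:1 on AUA risk group only, takes the first man with the right risk group who agrees, and then seeks no further match for that pair. Section 9.3 analyses every control who has RALRP. Section 9.5.1 compares mean EBL with a matched pairs t-test and no covariates.

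**The concern.** This is a non-randomized comparison of 10 pairs, so it depends on the two groups being alike before surgery. Risk group summarizes stage, PSA and Gleason score. It says nothing about the following criteria, which the plan uses to select PAE patients:

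- exclusion 17, "Coagulation disturbances not normalized by medical treatment";
- earlier pelvic irradiation or radical pelvic surgery (9, repeated as 14);
- earlier prostate surgery or other invasive prostate treatment (15 and 16);
- recent hospitalization for serious comorbidity (5) and low baseline hemoglobin (7);
- prostate size above 40 g (inclusion 5).

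If one arm is filtered on these and the other is not, a difference in EBL, operating time or margins mixes the effect of PAE with the effect of selection. In a proof-of-concept study the estimate is the main product, and it would carry that mixture forward.

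**Working it through.** **1. Do the criteria reach controls?**

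| Place | PAE patients | Controls |
|---|---|---|
| Section 3 heading | named | not named |
| 3.1 and 3.2 lead-ins | covered | covered if entry into the study includes controls |
| 4.1 / 4.2 | screening period to determine eligibility | risk-group match and agreement |
| 5.1, Visit -1 | all criteria | risk group |
| Schedule (A1 / A2) | eligibility row | matching row |

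Only the lead-ins point towards controls. No procedure carries the criteria out for them.

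**2. Stage.** The low-risk group is capped at T2a, and the intermediate group's stage term is T2b. Only the third group has no upper limit: "High risk: Stage T2c or higher tumors, OR PSA > 20ng/mL, OR Gleason score 8-10". A control beyond localized disease can therefore enter only a pair whose PAE patient is high risk.

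**3. Direction for EBL.** Section 1.2 links larger glands to more blood loss. Two opposing components follow:

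- *k* controls of a type excluded from the PAE arm bleed *a* SD more, which favours PAE;
- *m* controls with glands of 40 g or less bleed *b* SD less, which works against PAE.

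Bias in the mean paired difference (control minus PAE), in SDs of EBL, over 10 pairs:

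bias = (k·a − m·b) / 10

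The plan gives no EBL mean or SD, no gland-size distribution and no power calculation (9.2 says none was done), so there is no stated figure to reproduce. All four inputs are assumptions.

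| k | a | m | b | bias (SD) |
|---|---|---|---|---|
| 1 | 1 | 0 | – | +0.10 |
| 1 | 2 | 0 | – | +0.20 |
| 0 | – | 3 | 0.3 | −0.09 |
| 1 | 1 | 5 | 0.5 | (1 − 2.5)/10 = −0.15 |
| 2 | 1 | 5 | 0.5 | (2 − 2.5)/10 = −0.05 |
| 2 | 2 | 3 | 0.5 | (4 − 1.5)/10 = +0.25 |
| 0 | – | 5 | 1.0 | −0.50 |
| 3 | 2 | 0 | – | +0.60 |

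The last two rows are the extremes over k = 0–3, m = 0–5, a = 1–2 and b = 0.3–1.0. The sign changes within plausible inputs.

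**4. Effect on the test.** Assume two-sided 5%, no true effect and no within-pair correlation, so that the SD of the differences is √2 × SD. The noncentrality is (bias/√2)·√10 on 9 df. A bias of 0.2, 0.3 or 0.5 SD in either direction raises the rejection rate from 5% to about 6.9%, 9.2% or 17.1%.

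**5. One extreme control.** Suppose one pair differs by d and nine pairs by zero. The mean is d/10, the SD is d/√10 and the standard error is d/10, so t = 1 whatever d is, and p is about 0.34 on 9 df. The estimate moves; the test does not reach significance.

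**6. Direction for margins.** Section 1.2 reports more positive margins in glands under 50 g. Smaller control glands would therefore tend to favour PAE, as would higher stage in high-risk pairs. The two components do not offset each other here. The 40 g criterion does not separate the arms cleanly at 50 g, so no size is put on this.

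**The case against.** The strongest reply is that the lead-ins already cover everyone entered into the study, that 4.2 describes a similar cohort, and that controls consent and take part. That stands as far as it goes: a reader might infer that the criteria were deliberately confined to the PAE arm, and the text does not settle this. But if they were meant for controls, 5.1 and Appendix A2 omit the check, and the same amendment is needed.

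A reader might also infer that the gap biases blood loss in favour of PAE. The plan does not support that. A control who escapes the exclusions also escapes the >40 g criterion, and on section 1.2's own account smaller glands bleed less.

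Nor do all 20 exclusions matter. Numbers 9 and 14 are duplicates, several concern embolization alone, and controls must have an MRI anyway. Every control must also reach RALRP, after history, examination, CBC and PT, so some unsuitable men would probably not be operated on. That lowers the probability of the problem, which cannot be estimated from the plan. It does not remove it, because no stated rule acts on those results.

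Finally, matching on risk group alone is deliberate in a small proof-of-concept study, and 9.4 lists prostate size, staging, Gleason score and concurrent conditions as baseline characteristics. Imbalance would be visible, but the planned tests would not adjust for it.

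**Conclusion.** The point holds in a limited form. No procedure applies eligibility criteria to controls, the lead-ins of 3.1 and 3.2 disagree with that, and the unadjusted paired analysis cannot repair the resulting differences.

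For EBL the net direction is unknown: −0.50 to +0.60 SD under the assumed inputs. Two biases that may oppose each other are not a safeguard, since nothing makes them equal. For margins, both identifiable components tend towards PAE. For recurrence, the stage route is confined to high-risk pairs.

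A claim that a favourable EBL result could arise from selection alone goes too far if it rests on one unusual control, since that pattern gives t = 1. Any figure in cc would rest wholly on assumed blood losses. This is a worthwhile, inexpensive improvement to comparability; it does not show that the comparison is invalid.

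**What to change.** - Reconcile the heading of section 3 with the lead-ins of 3.1 and 3.2 by marking each criterion as applying to both groups or to PAE patients only.
- In 4.2, 5.1 and Appendix A2, require controls to meet the same age, localized-disease and >40 g criteria, and the non-embolization exclusions that bear on surgical outcome (for example 5, 7, 9/14, 15, 16 and 17). Prostate size must be included; without it the change would remove bias in one direction only.
- Add an eligibility assessment row to Appendix A2, to be completed before a match is accepted.
- Revise the statement in 4.2 that matches will be easy to find, since it rests on matching by risk group alone.

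The cost is a few lines of amendment. Control Visit -1 already collects demographics, history, concurrent conditions, CBC, PT, metabolic panel, DRE, TRUS and MRI, so no test is added and the sample stays at 10 + 10. The downside is that some candidate controls are passed over and control recruitment may be slower.

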### **Control Patients (Visit -1 must be within 12 weeks prior to RALRP):**

Prior to RALRP patients in the Control group will have the following assessments performed:

- Obtain Informed Consent
- Medical History, including demographics
- Physical exam, including vital signs, height (baseline only), weight, and genitourinary evaluation
- Assessment that patient is a match for a PAE patient based on:
  - Low, intermediate or high risk prostate cancer based on AUA guidelines
- Recording of concurrent medical conditions
- Recording of current medications
- Prostate Specific Antigen (PSA)
- Urinalysis
  - Specific gravity, protein, glucose, blood, leukocytes, nitrites
- Baseline blood tests
  - Complete blood count (CBC) including red blood count (RBC), white blood count (WBC), platelets, hemoglobin, hematocrit, neutrophils
  - PT (Prothrombin Time)
  - Comprehensive metabolic Panel
- Expanded Prostate Cancer Index Composite (EPIC) Questionnaire
- International Index of Erectile Function (IIEF) Questionnaire
- Digital Rectal Exam (DRE) and TRUS of the prostate
- MRI of the prostate

### **5.2 Visit 1: PAE Study Treatment (PAE patients only)**

PAE study treatment must be within 4 weeks of baseline MRI. PAE with Embosphere Microspheres will be performed following the procedure in Appendix C.

Treatment data recorded will include the following:

- Date of procedure
- Date and time of hospital admission and discharge
- Medications received immediately prior to and during the procedure
- Date and time of urinary catheter insertion and removal (if patient is discharged with catheter in place, catheter removal information will be collected at the first follow up visit)
- Medications at time of discharge
- Adverse events
- Fluoroscopy time and radiation dose

### **5.3 Visit 2: Post PAE, 2 weeks ( $\pm$ 4 days) from Visit 1 (PAE patients only)**

Patients in the PAE group will have the following assessments performed:

- Cystoscopy and proctoscopy will be performed: 1) if medically indicated, especially if there is pain out of proportion to that which is expected, 2) in all cases of bleeding per rectum, and 3) in cases of hematuria beyond that which is reasonably expected following prostatectomy.

### **5.4 Visit 3: Post PAE, 6 weeks ( $\pm$ 2 weeks) from Visit 1 (PAE patients only)**

Patients in the PAE group will have the following assessments performed:

- Physical exam including vital signs, weight, and genitourinary evaluation
- Blood and urine laboratory evaluations as at baseline
- Prostate Specific Antigen (PSA)
- DRE and TRUS
- MRI of the prostate
- Expanded Prostate Cancer Index Composite (EPIC) Questionnaire
- International Index of Erectile Function (IIEF) Questionnaire
- Adverse events
- Concomitant medications

Cystoscopy and proctoscopy will be performed: 1) if medically indicated, especially if there is pain out of proportion to that which is expected, 2) in all cases of bleeding per rectum, and 3) in cases of hematuria beyond that which is reasonably expected following prostatectomy.

### **5.5 Visit 4: Robot-Assisted Laparoscopic Radical Prostatectomy (RALRP) (10 weeks $\pm$ 2 weeks from Visit 1 for PAE patients and within 12 weeks of Visit -1 for Control patients):**

Patients in the PAE and Control groups will undergo RALRP and the following parameters will be recorded at the time of surgery and during the post-operative period:

- Date and time of hospital admission and discharge
- Date of procedure
- Time of first incision and closure time
- Estimated blood loss (EBL) during surgery (cc)
- Need for blood transfusion during surgery, including amount of transfusion
- Weight of the prostate (in grams) after its removal
- Pathology: complete/incomplete histological margin
- Pathology: presence of viable tumor
- Date and time of urinary catheter insertion and removal (if patient is discharged with catheter in place, catheter removal information will be collected at the first follow up visit)
- Concomitant medications
- Adverse events
- Complete blood count on day of RALRP prior to surgery
- Hemoglobin and hematocrit 1 day post-RALRP

Cystoscopy and proctoscopy will be performed: 1) if medically indicated, especially if there is pain out of proportion to that which is expected, 2) in all cases of bleeding per rectum, and 3) in cases of hematuria beyond that which is reasonably expected following prostatectomy

Patients in the PAE group will also have the following information recorded on pathology evaluation:

- Histology: distribution of embolic particles
- Histology: change in cancer morphology compared to pre-PAE biopsy
- Histology: change in normal prostate morphology compared to pre-PAE biopsy

